7.1.5.2. Incomplete Dates

If the onset date of an AE is incomplete and the AE stop date is not prior to the first dosing date of Run-in SEL, then the month and year (or year alone if month is not recorded) of onset will determine whether an AE is treatment emergent.

The event is considered treatment emergent to SEL exposure if both of the following 2 criteria are met:

- The AE onset date is the same as or after the month and year (or year) of the first dosing date of Run-in SEL, and
- The AE onset date is the same as or before the month and year (or year) of the 30th day after the last dosing date of SEL

An AE with completely missing onset and stop dates, or with the onset date missing and a stop date later than the first dosing date of Run-in SEL, will be considered to be treatment emergent to SEL exposure. In addition, an AE with the onset date missing and incomplete stop date with the same or later month and year (or year alone if month is not recorded) as the first dosing date of Run-in SEL will be considered treatment emergent to SEL exposure.

The event is considered treatment emergent to placebo exposure if both of the following 2 criteria are met:

- The AE onset date is the same as or after the month and year (or year) of the 30th day after the first dosing date of Randomized placebo (Study Day 31), and
- The AE onset date is the same as or before the month and year (or year) of the 30th day after the last dosing date of Randomized placebo

7.1.6. Summaries of Adverse Events and Deaths

Exposure-adjusted treatment-emergent AE incidence rates will be summarized based on the Safety Analysis Set, by exposure type (SEL or placebo) and overall. SEL exposure includes Run-in SEL exposure and Randomized SEL exposure.

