5. INVESTIGATIONAL MEDICINAL PRODUCTS

5.1. Randomization, Blinding and Treatment Codes

An Interactive Web Response System (IWRS) will be used to maintain a central log documenting screening, enrollment and randomization and study drug bottle numbers. It is the investigator's responsibility to ensure that the subject is eligible for the study prior to enrollment and randomization. Subjects will be assigned a screening number at the time of consent. Once eligibility for enrollment has been confirmed, the subjects will be assigned a unique subject number via IWRS and enter the Run-in period. During the Run-in, treatment will be unblinded and subjects will receive PTM for at least 7 consecutive days and SEL for at least 4 weeks. Subjects must be on SEL for at least 7 consecutive doses prior to Visit C and Visit 1 in order to randomize.

Subjects who meet randomization eligibility criteria will be randomized in a 1:1 ratio to either SEL or PTM. Randomization will be stratified by average eGFR values from Visit A and Visit B, average UACR values from Visit A and B, and concomitant use of SGLT-2 inhibitors at Visit 1. The unique subject number assigned at enrollment will remain the same in the randomized phase of the study.

- eGFR Strata:

eGFR strata (mL/min/1.73 m ²)
≥ 45
≥ 30 to < 45
≥ 15 to < 30

- Albuminuria Strata: UACR < 1500 mg/g vs. ≥ 1500 mg/g
- Concomitant SGLT-2 Inhibitor Use Strata: Yes vs. No

During the randomized phase, subjects and all personnel directly involved in the conduct of the study will be blinded to treatment assignment. Study drug will be dispensed in a blinded fashion to the subjects. Additionally, to maintain the blinding of treatment assignment, serum creatinine and eGFR results collected at Visits A, B, C, and 1 will not be released to subjects, investigators or sponsor before study unblinding, with the exception of eGFR values < 15 mL/min/1.73 m². The IWRS will be utilized to maintain the blinding of eGFR values required for stratification. A third party vendor, who is independent of Gilead, or Biometrics personnel at Gilead who are not associated with the study team will be unblinded to baseline eGFR values in order to monitor and calculate the decrease in eGFR of ≥ 40% relative to baseline.

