8.6. Safety Analysis

Safety will be assessed during the study through the reporting of AEs, and by clinical laboratory tests and vital sign assessments at various time points during the study. Concomitant medication usage will also be assessed throughout the study.

All safety data collected on or after the date that SEL or PTM was first dispensed up to the date of last dose of SEL or PTM plus 30 days, including data collected during the Run-in period, will be summarized by treatment group (according to the study drug received).

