3.1.5. Safety Analysis Set

The Safety Analysis Set includes all subjects who took at least 1 dose of Run-in SEL. This is the primary analysis set for safety analyses.

CCI

[REDACTED]

[REDACTED]

[REDACTED]

[REDACTED]

CCI

[REDACTED]

[REDACTED]

[REDACTED]

CCI

[REDACTED]

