3.2. Subject Grouping

For analyses based on the Full Analysis Set, subjects will be grouped according to the treatment to which they were randomized. For analyses based on the PP Analysis Set, subjects will be grouped according to the actual treatment received in the Randomization phase. For exposure-adjusted incidence rate (EAIR) analyses based on the Safety Analysis Set, subjects and events will be grouped according to exposure (SEL or placebo). Please refer to Section 7 for details on EAIR analyses. The actual treatment received will differ from the randomized treatment only when their actual treatment differs from randomized treatment for the entire treatment duration.

For the PK Analysis Set, subjects will be grouped according to the actual treatment they received.

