7.1.5. Treatment-Emergent Adverse Events

7.1.5.1. Definition of Treatment-Emergent Adverse Events

Treatment-emergent adverse events (TEAEs) are defined as follows for SEL and placebo exposures, respectively.

- SEL exposure: TEAEs are defined as 1 or both of the following:
 - Any AEs with an onset date on or after the Run-in SEL start date and no later than 30 days after permanent discontinuation of SEL
 - Any AEs leading to premature discontinuation of SEL

- Placebo exposure: TEAEs are defined as any AEs with an onset date on or after Study Day 31 (30 days after the Randomized placebo start date) and no later than 30 days after permanent discontinuation of Randomized placebo

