7.1.6.1. Calculation of Treatment Exposure

Treatment exposure will be calculated as follows, for SEL and placebo respectively:

- SEL: Total exposure (Patient Year) is calculated as the sum of Run-in SEL and Randomized SEL exposure time (in years) for all subjects who have been exposed to Run-in SEL and/or Randomized SEL in the Safety Analysis Set, starting from the first dosing date of Run-in SEL to the last dosing date of SEL (Run-in SEL or Randomized SEL).

In other words,

Total SEL Exposure

$$\begin{aligned}
 &= \sum_{i \in \{\text{Subjects randomized to SEL}\}} \text{Ex}(\text{first dose of Runin SEL to last dose of Randomized SEL})_i \\
 &+ \sum_{i \in \{\text{Subjects randomized to Placebo}\}} \text{Ex}(\text{first dose of Runin SEL to last dose of Runin SEL})_i \\
 &+ \sum_{i \in \{\text{Subjects not randomized}\}} \text{Ex}(\text{first dose of Runin SEL to last dose of Runin SEL})_i
 \end{aligned}$$

- Placebo: Total exposure (Patient Year) is calculated as the sum of Randomized placebo exposure time (in years) for all subjects who exposed to Randomized placebo in the Safety Analysis Set, starting from Study Day 1 to the last dosing date of Randomized placebo.

In other words,

Total Placebo Exposure

$$= \sum_{i \in \{\text{Subjects randomized to Placebo}\}} \text{Ex}(\text{first dose of Randomized Placebo to last dose of Randomized Placebo})_i$$

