7.7. Changes From Protocol-Specified Safety Analyses

There are no deviations from the protocol-specified safety analyses.

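### The SAP's adverse event rate tables set pooled run-in and randomized SEL against randomized placebo only, with event windows that do not match the exposure time

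*SAP*

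**What the plan says.** SAP 7.1.6 to 7.1.6.3 presents TEAEs, SAEs, treatment-related AEs, AEs leading to discontinuation and deaths as exposure-adjusted rates by exposure type and overall. On the SEL side, "SEL exposure includes Run-in SEL exposure and Randomized SEL exposure". SAP 7.1.6.1 totals this "for all subjects who have been exposed to Run-in SEL and/or Randomized SEL in the Safety Analysis Set"; its formula has one term each for the SEL arm, the placebo arm (run-in SEL only) and non-randomized subjects. Protocol 5.1 states that "During the Run-in, treatment will be unblinded". The placebo total is randomized placebo alone, counted from Study Day 1.

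The event windows are in SAP 7.1.5.1. SEL events run from the first run-in SEL dose to 30 days after SEL stops. For placebo, "TEAEs are defined as any AEs with an onset date on or after Study Day 31", ending 30 days after the last randomized placebo dose. SAP 7.2.2.1 to 7.2.3 apply the same split to graded laboratory abnormalities and liver thresholds.

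Protocol 8.6 covers safety data from first dispensing of SEL or PTM and says that these, "including data collected during the Run-in period, will be summarized by treatment group", according to the drug received. Protocol 8.6.2 plans numbers and percentages of subjects with TEAEs by treatment group. SAP 7.7 says: "There are no deviations from the protocol-specified safety analyses".

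**The concern.** Safety and tolerability are a secondary objective, and these are the main safety tables. Their two columns differ in more than drug. One includes weeks when investigators judging relatedness knew the tablet was SEL, and includes subjects who failed run-in. The other is entirely blinded and limited to subjects who had already completed SEL run-in. Subjects randomized to placebo appear in both.

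The counting rules add a second problem. A placebo-arm subject's events on Study Days 1 to 30 fall within 30 days of the last run-in SEL dose, so they enter the SEL numerator, while those days enter the placebo denominator. The placebo arm's Week 4 laboratory sample, nominal Study Day 29 in SAP Table 3-2, falls under SEL in the same way. A SEL excess could then appear with no drug effect, and a real one could not be separated from it.

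**Working it through.** The plan gives no expected rate or ratio here, so there is no figure to reproduce. The check applies the SAP's formulas to two arms with the same constant hazard, so that the true ratio is 1.

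Inputs from the documents:
- 150 per arm (SAP 1.3).
- Run-in SEL r = 28 to 42 days: Visit B to C is 21 to 28 days, and Visit C to Visit 1 is 7 to 14 (Protocol Appendix 2).
- Post-dose window w = 30 days = 0.0821 years.
- Phase 2 placebo frequencies over 48 weeks: 18.8% for SAEs and 83.5% for any AE (Protocol 1.2.3.2.4).

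Assumptions:
- Everyone completes T = 48 to 96 weeks of randomized dosing.
- F = 0 to 75 subjects take run-in SEL but are not randomized.

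Hazards: λ = −ln(1 − p)/0.9199 years, which gives 0.2264 per year for SAEs and 1.959 for any AE.

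Formulas, with P(t) = 1 − exp(−λt):
- SEL subjects with an event: 150·P(r+T+w) + (150+F)·P(r+w)
- SEL exposure: 150(r+T) + (150+F)r
- Placebo subjects with an event: 150·P(T), because Day 31 to T + 30 days has length T
- Placebo exposure: 150T

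Worked case: SAEs, r = 28 days (0.0767 years), T = 48 weeks (0.9199 years), F = 0.
- SEL events: 150·P(1.0787) + 150·P(0.1588) = 32.50 + 5.30 = 37.80
- SEL exposure: 149.49 + 11.50 = 160.99 patient-years, so 23.48 per 100
- Placebo: 28.20 events in 137.99 patient-years, so 20.44 per 100
- Ratio: 23.48/20.44 = 1.149

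Of the 5.30 events from the placebo arm, 150·P(0.0767) = 2.58 arise during run-in SEL. The other 2.72 arise in the first 30 days on blinded placebo.

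To isolate pooling, end each SEL window at the last dose (w = 0). SEL events become 32.88, the rate is 20.42 and the ratio is 0.999.

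| Event | r (days) | T (weeks) | F | SEL rate | Placebo rate | Ratio | Pooling only |
|---|---|---|---|---|---|---|---|
| SAE | 42 | 96 | 0 | 19.96 | 18.52 | 1.078 | 1.000 |
| SAE | 28 | 48 | 75 | 24.26 | 20.44 | 1.187 | 1.003 |
| Any AE | 42 | 48 | 0 | 105.07 | 90.77 | 1.158 | 1.025 |
| Any AE | 42 | 96 | 75 | 68.72 | 52.87 | 1.300 | 1.139 |

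Rates are per 100 patient-years. The rows are the lowest and highest as-planned ratios for each event type over the ranges above. Across the same ranges pooling alone gives about 1.00 for SAEs and 1.02 to 1.14 for any AE.

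Two mechanisms are at work:
- Windows. Both columns gain a 30-day tail with no matching time. Placebo gives 30 days back at the start, while SEL gives back nothing and takes a tail from every placebo-arm and non-randomized subject.
- Common events. Subjects with an event are divided by total exposure, which does not stop at the first event, so the rate falls as follow-up lengthens. At least half the SEL column contributes only 4 to 6 weeks: 150 of 300 subjects with F = 0, and 225 of 375 with F = 75.

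Run-in supplies (300+F)r of the SEL patient-years: 14% to 24% at 48 weeks and 8% to 14% at 96 weeks. If both arms were counted from first randomized dose to last dose + 30 days, each rate would be P(T+w)/(T+w) and the ratio 1.00.

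**The case against.** The strongest defense is Protocol 8.6, which groups run-in data by drug received. Counting a placebo-arm subject's run-in SEL events under SEL is a fair reading of that, and intolerance that ends in run-in failure is a SEL effect that should be visible. Both points stand. The 30-day rule also has a carry-over rationale. It does not explain why person-time is not moved along with the events.

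Three stronger readings are tempting, and the documents do not support them:
- A reader might infer that safety is never compared between the arms. AEs of special interest (SAP 7.1.7), numeric laboratory results (7.2.1), vital signs (7.3) and ECGs (7.5) are by treatment group. The gap is in the AE-rate, graded-laboratory and liver tables. SAP 7.1.7 covers only three AE categories and states no restriction to the blinded phase.
- A reader might infer that every enrolled subject enters the SEL column. SAP 3.1.5 is narrower: "The Safety Analysis Set includes all subjects who took at least 1 dose of Run-in SEL".
- A reader might blame the pooling itself, supposing that event rates in the run-in weeks are 1.5 to 2 times later ones. That would give ratios of 1.04 to 1.24 before any window effect, but no passage supports such an early excess. At a constant hazard, pooling does almost nothing to SAE rates.

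It can also be said that the error runs against SEL, so it is likelier to overstate harm than hide it. Under constant hazards that is right, but the rates still cannot be read as a drug effect.

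**Conclusion.** Wrong as written. The main AE-rate, graded-laboratory and liver tables do not compare the randomized arms over a common blinded window, and their numerators and denominators cover different periods. With no drug effect the expected SEL/placebo ratio is about 1.08 to 1.19 for SAEs and 1.16 to 1.30 for any AE. For SAEs nearly all of this comes from the window mismatch; for any AE, pooling also contributes. These figures illustrate the rules and do not forecast the trial. They rest on constant equal hazards, complete follow-up, Phase 2 placebo frequencies and an assumed number of run-in failures.

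The statement in SAP 7.7 is inaccurate. Grouping by drug received has some basis in Protocol 8.6. Replacing the by-group TEAE counts and percentages of Protocol 8.6.2, and leaving run-in PTM out of the rates, are undeclared changes.

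**What to change.** - Add TEAE, SAE, treatment-related AE, discontinuation and laboratory-abnormality tables by randomized arm for the double-blind phase. Use first randomized dose to last dose + 30 days in both arms, with exposure time matched to that window.
- Add a Day 31 start in both arms as a sensitivity analysis for SEL carry-over. It should not be the main window, because it discards 30 days of valid blinded SEL exposure.
- Report run-in SEL and run-in PTM as separate open-label columns, so that early SEL intolerance stays visible.
- Keep the pooled SEL rate as supportive, with its event and exposure windows aligned. For common events alignment does not remove the effect of unequal follow-up, so this rate should not carry the comparison.
- List these changes in SAP 7.7.

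The cost is SAP wording and more table columns; no new data are needed. The by-arm tables cover only subjects who completed SEL run-in, have fewer SEL person-years, and may include some SEL carry-over in the placebo arm's first month.

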Due to this acute (potentially artefactual) effect observed in prior studies, this Phase 2b study has incorporated a Run-in design to account for the acute eGFR effect in order to better characterize the chronic (long-term) effect of SEL on eGFR. To maintain the integrity of the study, other than eGFR values < 15 mL/min/1.73 m², eGFR results collected at Visits A, B, C, and Visit 1 will not be released to subjects, investigators or sponsor before study unblinding. All eGFR values starting at week four will be released to subjects, investigators and the sponsor for safety monitoring and treatment decisions.

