6.4.12. Estimated Glomerular Filtration Rate

- Screening: Subjects can have up to 3 eGFR collections during the Screening period. Any one of the eGFR values and any one of the UACR values collected during Screening may be used to satisfy the inclusion criteria. Subjects must have an eGFR value calculated by central laboratory utilizing samples collected during Screening and prior to Enrollment (Visit A) of ≥ 20 mL/min/1.73 m² to < 60 mL/min/1.73 m².
- Run-in period: Other than eGFR values < 15 mL/min/1.73 m², eGFR and serum creatinine results collected at Visit A, B, C, and Visit 1 will not be released to subjects, investigators or sponsor before study unblinding. Local labs assessing eGFR or creatinine should not be collected during the Run-in period or during the time after the Run-in period leading up to the Week 4 visit unless required for safety.
- Run-in prior to Week 4: If there is a $\geq 50\%$ decline in eGFR compared to Screening during the Run-in period prior to Week 4, a central laboratory flag will be issued to notify the site of this drop. Sites will be notified of the $\geq 50\%$ eGFR decline but will continue to be blinded to the eGFR values. Local labs assessing eGFR or creatinine should not be collected during the Run-in period or during the time after the Run-in period leading up to the Week 4 visit unless required for safety.

- Randomization: Subjects must have eGFR values of ≥ 15 mL/min/1.73 m² at all central laboratory assessments during the Run-in period to satisfy randomization eligibility.
- Stratification: eGFR will be the average of Enrollment (Visit A) and Visit B measurements. This value will be transferred directly from the central laboratory to the IWRS system for stratification.

A clinical endpoint event is a confirmed decrease in eGFR to < 15 mL/min/1.73 m² for subjects who remain asymptomatic without initiation of dialysis or kidney transplantation. The eGFR confirmatory measure will be collected at the next scheduled study visit but at least 4 weeks after the index measurement.

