8.9. Sample Size

8.9.1. Sample Size Determination

With a sample size of 300 subjects (150 per treatment arm), power to detect a difference in $eGFR_{cr}$ decline rate of 3.7 mL/min/1.73 m²/year (common SD = 10 mL/min/1.73 m²/year) between SEL 18 mg and placebo using a two-sample t-test is 99% at a 1-sided significance level of 0.15. Assuming 15% dropout, with a sample size of 254 (127 per arm), the power is 97%.

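### Creatinine-triggered renal AEs may be under-ascertained in part of the SEL person-time, and the planned SEL versus placebo rate cannot show which way the net bias runs

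*SAP*

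**What the plan says.** **Masking.** Protocol 6.4.12 states that, other than eGFR below 15, "eGFR and serum creatinine results collected at Visit A, B, C, and Visit 1 will not be released to subjects, investigators or sponsor" before unblinding. The same section has the central laboratory flag to the site a fall of 50% or more from Screening before Week 4, without giving the value. It discourages local eGFR or creatinine tests until the Week 4 visit unless safety requires them. Protocol 1.3 then opens the data: "All eGFR values starting at week four will be released to subjects, investigators and the sponsor for safety monitoring and treatment decisions".

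**Exposure.** SAP 7.1.6 says "SEL exposure includes Run-in SEL exposure and Randomized SEL exposure". SAP 7.1.6.1 counts SEL time "starting from the first dosing date of Run-in SEL to the last dosing date of SEL", and does so for subjects randomized to SEL, randomized to placebo or never randomized. Placebo time runs from Study Day 1.

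**Events.** Under SAP 7.1.5.1, SEL events count from the first run-in SEL dose to 30 days after SEL is permanently stopped. Placebo events count only from Study Day 31.

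**Where renal terms appear.** They enter the exposure-adjusted tables by system organ class and preferred term (SAP 7.1.6.3). The Acute Renal Failure category in SAP 7.1.7 is number and percentage by treatment group. Creatinine and cystatin C grades in SAP 7.2.2 come from central laboratory data, whether or not the site saw them.

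**The concern.** Under Protocol 7.1.3 a laboratory abnormality must be recorded as an AE if it leads to intervention or discontinuation, or if it comes with signs or symptoms and meets the AE definition. A value that the investigator does not see cannot prompt the first two. The masked weeks are also when SEL's acute eGFR effect appears. Protocol 7.5.5 gives a median fall of 10% at Week 4 on 18 mg in the Phase 2 study, and 19% or more in about a quarter of subjects. A fall of 19-49% that leaves eGFR at 15 or above triggers neither release nor flag.

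In placebo-randomized subjects the effect may be gone by the first released result: in the Phase 1b study (Protocol 1.2.3.1) it had reversed after a 28-day washout. Subjects who leave during run-in may never reach a released result. Their run-in time still sits in the SEL denominator.

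At stake is how the aggregate renal AE tables are read. Phase 2 reported acute kidney injury in 7.2% on 18 mg and 2.4% on placebo (Protocol Table 1-4). The aggregate tables matter more because creatinine and GFR SAEs are generally exempt from expedited reporting (Protocol 7.4).

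**Working it through.** **The plan's own figure.** The documents give no renal AE rate or exposure total. The only design figure is power (Protocol 8.9.1), used here only to confirm the arm size. For 150 per arm, a difference of 3.7 and an SD of 10, the power "is 99% at a 1-sided significance level of 0.15". Normal approximation: 3.7 / (10 × √(2/150)) = 3.204; 3.204 − 1.036 = 2.168; power 98.5%. With 127 per arm it is 97.2%. Both agree with the stated 99% and 97%.

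**Share of SEL time where detection may fail for good.** Assume 150 per arm, 5 weeks of run-in SEL, R randomized weeks, and n non-randomized subjects with 3 weeks each.

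Share = (150×5 + 3n) / (150×(5+R) + 150×5 + 3n)

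- R = 84, n = 0: 750 / 14,100 = 5.3%
- R = 48, n = 60: 930 / 8,880 = 10.5%

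**Placebo's own loss.** Thirty days of placebo time carry no countable event: 30/336 = 8.9% at 48 weeks and 30/588 = 5.1% at 84. The placebo rate is therefore 0.911 or 0.949 of true. Setting the two losses against each other at the same R and equal hazards:

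- R = 48, n = 60: 0.895/0.911 = 0.98
- R = 84, n = 0: 0.947/0.949 = 1.00

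**Range of the SEL/placebo ratio.** Inputs:

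- run-in SEL of d = 28 to 42 days (visit windows, Protocol Appendix 2)
- F = 336 randomized days (the 48-week minimum) or 588 (the Week 84 horizon in SAP 6.1.1)
- n = 0 or 30 non-randomized subjects, each given the full d days
- equal constant hazards and rare events

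SEL time is D = d(300 + n) + 150F. Each SEL fraction below is divided by the placebo fraction (F − 30)/F.

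| Case | SEL fraction of true rate | Ratio, 48 wk | Ratio, 84 wk |
|---|---|---|---|
| (a) every event before Week 4 lost | 150(F − 28)/D | 0.79-0.86 | 0.87-0.92 |
| (b) every run-in event lost | 150F/D | 0.86-0.94 | 0.91-0.96 |
| (c) run-in events lost only in placebo-randomized and non-randomized subjects | [D − d(150 + n)]/D | 0.97-1.02 | 0.98-1.01 |
| (d) run-in events detected, and Days 1-30 of placebo-randomized subjects counted to SEL | (D + 30×150)/D | about 1.18 | about 1.10 |

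Two ends in full, at 48 weeks:

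- (a), d = 42, n = 30: D = 13,860 + 50,400 = 64,260; 46,200/64,260 = 0.719; 0.719/0.911 = 0.79.
- (d), d = 28, n = 0: D = 58,800; 63,300/58,800 = 1.077; 1.077/0.911 = 1.18.

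These cases leave out the 30 days after the last randomized dose. If every subject contributed them, the placebo fraction would become (F − 30 + 30)/F = 1 and the SEL arm would gain 30×150 days. At 48 weeks case (a) stays at 0.79-0.86. Case (c) becomes [D − d(150 + n) + 4,500]/D = 0.95-1.01. Case (d), with the post-SEL window of non-randomized subjects also counted, becomes 1.14-1.17.

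**The case against.** **The stronger reading.** A reader might infer that renal AEs cannot be seen at all in run-in, and that the SEL rate is therefore diluted, by up to a quarter, against a placebo rate taken under full visibility. The same share formula with all SEL time before Week 4 in the numerator (150×9 + 150×5 + 3n) does give 15-26%. The documents do not support that reading.

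- Masking is incomplete, given the three exceptions. It names only eGFR and serum creatinine. Chemistry drawn at the same visits includes BUN, potassium, bicarbonate and cystatin C (Protocol Appendix 3), and nothing says these are withheld. Symptomatic kidney injury remains reportable.
- A fall that persists to Week 4 in a SEL-randomized subject is found late, not lost, and the rate counts subjects with at least one event. The 15-26% treats delay as loss.
- The placebo rate carries its own dilution, and masking from Day 1 to Week 4 applies to both arms.
- The 30-day SEL window adds events without SEL time, including AEs in a placebo-randomized subject's first weeks on placebo.
- The Phase 2 kidney injury figures cover the whole study, with nothing to show that the events were early or found only by laboratory values. Serious cases were 1.2% on 18 mg and 2.4% on placebo (Protocol Table 1-5).
- Laboratory changes without clinical significance are not AEs (Protocol 7.1.3), so many acute falls would go unreported even if seen.

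**What remains.** Case (d) fits AEs reported on symptoms better than terms found only through creatinine. For those terms cases (a) to (c) are closer, and most of their range lies below 1. That makes some lowering plausible but does not prove it. The Acute Renal Failure percentages avoid the person-time problem, but not missed detection. The central-laboratory grades avoid missed detection, although their exposure-adjusted rate (SAP 7.2.2.3) inherits the unequal windows.

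**Conclusion.** The point holds as one of unequal ascertainment, not of proven dilution. Laboratory-triggered renal AEs may be under-ascertained in part of the SEL person-time, mainly the run-in time of placebo-randomized and non-randomized subjects. That is about 5-10% of SEL exposure under the stated assumptions.

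The direction of the net SEL versus placebo bias is undetermined. Across the scenarios the ratio could run from about 0.79 to about 1.18 with no true difference. It is about 0.97-1.02 if only the run-in events of placebo-randomized and non-randomized subjects are lost, or 0.95-1.01 at 48 weeks with the closing 30-day window included. All of this assumes equal constant hazards. If SEL's risk is concentrated after initiation, the loss on SEL would be larger. The planned table is not invalid, but it should not be read alone for creatinine-dependent terms. The remedy is cheap enough to justify on that basis.

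**What to change.** 1. Keep the planned exposure-adjusted rates in SAP 7.1.6.
2. For creatinine- or eGFR-dependent terms (acute kidney injury, blood creatinine increased, GFR decreased, renal impairment), add one table restricted to randomized SEL and randomized placebo. Count both events and exposure from Study Day 31 in both arms, or from each subject's first released result. Choose one start before unblinding, because they differ: the Week 4 window is ±5 days, so Day 31 does not guarantee that a result has been released, while a start at the first result can admit a fall found at that visit.
3. Close the events and exposure at the same point in both arms, so that no window counts events without time.
4. Footnote the planned table to say that investigators were largely masked to creatinine and eGFR before Week 4. For run-in renal safety, refer to the central-laboratory creatinine and cystatin C grades already planned in SAP 7.2.2.

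The cost is SAP wording, one table and a footnote, with no new data. The drawback is that the added table leaves out the SEL-initiation weeks and includes only subjects who passed run-in, so it could understate renal harm on SEL. It must stand beside the planned rate, with renal AEs before its start shown separately.
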